### 3.1.3.2 Pharmacokinetic endpoints for 3BP-227

The following PK parameters will be derived by NCA of the plasma concentration-time profiles during cycle 1:

- $C_{\max}$  (ng/mL): Maximum observed 3BP-227 plasma drug concentration;
- $\text{AUC}_{0-t_{\text{last}}}$  (ng/mL\*h): Area under the plasma concentration-time curve of 3BP-227 from start of infusion to time t corresponding to the last quantifiable concentration
- $\text{AUC}_{0-\infty}$  (ng/mL\*h): Area under the plasma concentration-time curve of 3BP-227 from start of infusion to infinity calculated as follows:

$$\text{AUC}_{0-\infty} = \text{AUC}_{0-t_{\text{last}}} + C_{\text{last}}/\lambda_z,$$

with  $C_{\text{last}}$  as the last quantifiable concentration

- $t_{1/2}$  (h): Terminal elimination half-life calculated as follows:

$$t_{1/2} = \text{Ln}(2)/\lambda_z$$

- CL (L/h): Total clearance from plasma calculated as follows:

$$CL = \text{Dose} / AUC_{0-\infty}$$

- $V_z$  (L): Volume of distribution from plasma calculated as follows:

$$Vd_z = CL / \lambda_z$$

- MRT (h): Mean residence time

$$MRT = AUMC_{0-\infty} / AUC_{0-\infty}$$

with  $AUMC_{0-\infty}$ : Area under the first moment curve from zero to infinity

The following PK parameters will be derived by NCA of the individual urine concentrations:

- $C_i \times V_i$  (ng) at each time interval with  $C_i$ : concentrations and  $V_i$ : collected volume
- $A_e$  (ng): Cumulative amount of drug excreted in urine during 48 hours, calculated as follows:

$$A_e = \sum C_i \times V_i$$

- $F_e$  (%): fraction of the administered drug excreted in urine during 48 hours
- $CL_R$  (L/h): Renal clearance calculated as follows:

$$CL_R = A_e / AUC_{0-\text{last}}$$

### 3.1.3.3 Radiation dosimetry endpoints for $^{177}\text{Lu}$ -3BP-227

The following parameters will be evaluated (only in organs and target lesions showing uptake):

- Organs receiving the highest absorbed dose by cycle;
- Specific absorbed dose to the target lesions (Gy/GBq) by cycle;
- Specific absorbed dose per organ (Gy/GBq) by cycle;
- Time-Integrated Activity Coefficient (TIAC) (or residence time) per organ and to the target lesions by cycle;
- Whole body effective dose (Sv)
- Whole body effective dose per administered activity (Sv/GBq)
- Absorbed doses on cycle 1 and cumulative absorbed doses on cycles 1 and cycle 2 per organ and to the target lesions (Gy).

The absorbed dose to the target lesions and discernible organs (i.e. organs showing uptake) will be evaluated by image-based analysis. It relies on the visual identification of the regions of interest on the images and determination of activity and absorbed doses using Planet Dose solution (Dosisoft). The organs considered for  $^{177}\text{Lu}$ -3BP-227 image based dosimetry assessment will be the following: Healthy Liver, Total Liver, Bone marrow, Left Kidney, Right Kidney, Intestine (large & small), Spleen, Pancreas, Stomach wall, Right ovary, Left ovary, Uterus, Right testis, Left testis, Thymus, Right thyroid gland, Left thyroid gland, Prostate gland and total body. Additional organs may be added later on.

In addition to the image-based analysis, the absorbed doses of all organs will be evaluated by model-based analysis (OLINDA/EXM version 1.0) using TIAC estimates from the image-based analysis.

Effective dose will be evaluated by model-based analysis.

Finally, absorbed dose in red marrow will also be computed assuming proportionality on activity measures in blood samples (blood based method).

Absorbed doses and specific absorbed doses will be also presented on kidney (left+right) using the average of left kidney and right kidney.

Details on the different calculations are provided in the Dosimetry Analysis Plan of the study.

### **3.1.4 Exploratory endpoints**

Exploratory endpoints will be described in a dedicated SAP.

### **3.1.5 Multiplicity**

There is no plan for multiple testing adjustments in this study.

### **3.1.6 Significance testing and estimation**

All statistical tests will be one-sided at the 5% level of significance.

## **3.2 Analysis methods**

### **3.2.1 Safety**

All safety data will be included in the data listings and summary tables will be based on the safety population.

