### 1.2 Study design

This is a multicentre, open-label phase I/II study of  $^{177}\text{Lu}$ -3BP-227 in subjects with unresectable, locally advanced or metastatic solid tumours expressing NTSR1 who have exhausted their available standard-of-care treatment options and/or are deemed suitable for treatment with  $^{177}\text{Lu}$ -3BP-227 as per the investigator's clinical assessment and/or their individual disease state. The study consists of a phase I with a dose escalation part (and potential expansion cohorts) and a phase II either in selected or over multiple indications in a basket approach. The purpose of the radioactivity escalation part is to determine the maximum tolerated cumulative (MTCA).

During phase I, it is planned to enrol subjects with unresectable, locally advanced, or metastatic tumours expressing NTSR1 originating from either the:

[figure not shown]
- Pancreas (Pancreatic Ductal Adenocarcinoma, PDAC);
- Colon and rectum (Colorectal Cancer, CRC);
- Stomach (Gastric Cancer, GC);
- Gastrointestinal Stromal Tumours, (GIST);

- Head and neck region (Squamous-Cell Carcinoma of Head and Neck, SCCHN);
- Bone (Ewing Sarcoma, ES).

Following eligibility confirmation, it is anticipated that a maximum of 30 subjects will receive the Lu-3BP-227 therapeutic dose in up to six cohorts with four escalation steps. Three to five subjects will be treated per cohort in order to yield a minimum of three evaluable subjects per radioactivity level, treated at the full planned radioactivity amount fractionated into two administrations. Once five subjects are enrolled in a cohort, the enrolment will be stopped in that cohort. Once the dose escalation part has been completed, the MTCA level may be repeated in an additional cohort.

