### 1.3.4 **Planned sample size**

As this is primarily a descriptive safety and tolerability study, the total number of subjects is not based on a formal statistical sample size calculation.

The actual sample size required to adequately determine the MTCA/ Maximum Tolerated Single Activity (MTSA) during dose escalation depends on the initial dose, rate of dose escalation and the observed dose-toxicity and dose/radiation exposure relationships. Simulation studies have been performed to quantify the operational characteristics (i.e. precision of the MTCA/MTSA, sample size, number of subjects being over/under dosed) of the adaptive dose-escalation design under a number of plausible dose-DLT relationship scenarios. Based on experience, the chosen sample size of three to five subjects per cohort is considered sufficient to fulfill the objectives of the study. It is anticipated that approximately 30 subjects will be required to establish the MTCA or Maximum Administered Cumulative Activity (MACA).

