### 2.3 **Safety population**

The safety population is all subjects who received at least one dose of study medication (including screening administration).

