## 2.7 **Primary population**

The primary objective of this study is safety and tolerability, therefore the primary population for analysis is the safety population.

The pharmacodynamics/efficacy analyses will be based on the pharmacodynamic population, except analyses on tumour response which will be based on the primary pharmacodynamic population and overall survival which will be based on the included population.

The Lu-3BP-227 blood pharmacokinetic analyses will be based on the Lu-3BP-227 blood Pharmacokinetic population.

The Lu-3BP-227 urine pharmacokinetic analyses will be based on the Lu-3BP-227 urine Pharmacokinetic population.

The 3BP-227 plasma pharmacokinetic analyses will be based on the 3BP-227 plasma Pharmacokinetic population.

The 3BP-227 urine pharmacokinetic analyses will be based on the 3BP-227 urine Pharmacokinetic population.

The Lu-3BP-227 pharmacokinetic analyses in discernible organs and target lesions will be based on the dosimetry population.

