#### 3.1.1 **Safety endpoints**

The safety endpoints are:

- Treatment Emergent Adverse Events (TEAEs), including information on seriousness, intensity, drug relationship and DLTs;
- Clinical laboratory evaluations for haematology, biochemistry, urinalysis, hormones and shift tables;
- Clinical safety endpoints: physical examination, vital signs, body weight, BMI, 12-lead ECGs, 24h 3-lead holter ECGs, serum and urine pregnancy tests, ECOG and specific renal safety biomarkers.

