A TEAE for the long-term follow-up period is defined as any AE that occurs during the long-term follow-up period of the study if:

- It was not present prior to EOCT/ED visit or EOAC/ED visit, or
- It was present prior to EOCT/ED visit or EOAC/ED visit but the grade increased between EOCT/ED visit or EOAC/ED visit and end of study,
- It was present prior to EOCT/ED visit or EOAC/ED visit, the grade is the same but the causality changed to “related” between EOCT/ED visit or EOAC/ED visit and end of study.

In addition, adverse events will be assigned to a specific cycle of treatment for core trial and additional cycles. This assignment will be based on the start date of the adverse event: if the AE start date is on or after the date of treatment X and before the date of treatment X+1 (or if the subject does not receive a treatment X+1 or the treatment X+1 date is missing), then the TEAE will be assigned to Treatment Cycle X.

An overall summary table of all AEs will be presented by treatment group and overall, by cycle (if applicable) and overall, after IMP screening administration, for core trial, additional cycles and follow-up long term separately. In addition, an overall summary table will be presented by pooling cycles from core trial and additional cycles.

TEAEs will be summarised by treatment group and overall with the number and percentage of subjects with AEs classified by primary system organ class and preferred term, by cycle (if applicable) and overall, after IMP screening administration, for core trial, additional cycles and follow-up long term separately. The number of occurrences of a TEAE will also be presented.

In addition, summary tables will also be presented for related TEAEs, SAEs, related SAEs, non-serious TEAEs, TEAEs by decreasing frequency, TEAEs by NCI-CTCAE worst grade (for NCI-CTCAE worst grade  $\geq 3$ ) and TEAEs by most serious causality (category related only).

Summary of TEAEs and related TEAEs will be also summarised by pooling cycles from core trial and additional cycles.

DLTs during cycle 1 or 2 (i.e. occurring between the first administration of Lu-3BP-227 and EOCT/ED) will be summarised by treatment group and overall with the number and percentage of subjects with DLTs classified by primary system organ class and preferred term. The number of occurrences of a DLT will also be presented.

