### **3.2.22 Rules and data formats**

Data will be presented using an appropriate number of decimal places (i.e. the number of decimal places used does not imply undue precision). Raw data will be presented with the number of decimal places collected, and derived data will be presented to an appropriate number of decimal places. The appropriate number of decimal places will be determined by general practice, mathematical rationale or scientific rationale (e.g. age should be presented in whole numbers).

For PK/dosimetry data, all values will be reported with 3 significant digits for numbers < 1000, otherwise values will not be rounded.

For summary statistics, the following will be presented: n, arithmetic mean, standard deviation, median and the range (minimum, maximum).

Mean, median and standard deviation values will be reported with one decimal place greater than the raw/derived data that they summarise. Minimum and maximum values will be reported with the same precision as the raw data.

Percentages will be reported with 1 decimal place and 0% will not be presented. Percentages will be calculated using a denominator of all subjects in a specified population and by treatment group. The denominator will be specified in a footnote to the tables for clarification if necessary.

All values below or above a limit of quantification (e.g. < 0.1 or > 100) will be listed as such. For each safety parameter for which it is possible to have values below or above LOQ, the rule to be used in the statistical tables is to replace values below or above a limit of quantification by LOQ.

All text fields must be left justified and numeric or numeric with some text specification (e.g. not done, unknown, < 4.5, ...) must be decimal justified. Dates will be presented in the format [yyyy-mm-dd] and times in the format [hh:mm].

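### The visible SAP has no analysis set for the MTCA/MTSA evaluation, no final MTCA/MTSA analysis and no reporting of MTCA or MACA, the protocol's primary endpoint, and declares no change

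*SAP*

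**What the plan says.** **Protocol.** Section 4.4.1.1 makes MTCA the primary endpoint of dose escalation, with MACA as the fallback if MTCA is not identified. Section 12.1 limits the MTCA and MTSA (maximum tolerated single activity) evaluations to subjects who finish Cycle 2 and those whose participation ends in either cycle because of a DLT. Section 12.2.4 plans DLT listings and incidence. Where feasible, it adds a Bayesian logistic model fitted with both moderately informative and noninformative priors, 90% credibility sets, MTCA and MTSA derived from the model, and posterior tables and graphs. Section 12.2.2 leaves analysis detail to the SAP and calls for exact 95% confidence intervals on categorical data.

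**SAP.** The SAP covers dose escalation only. Section 1.2 says: "The purpose of the radioactivity escalation part is to determine the maximum tolerated cumulative (MTCA"). Section 1.3.4 gives the reason for the planned number: "It is anticipated that approximately 30 subjects will be required to establish the MTCA or Maximum Administered Cumulative Activity (MACA"). Section 2 defines screened, included, safety, pharmacodynamic, pharmacokinetic and dosimetry sets. Section 2.7 states: "The primary objective of this study is safety and tolerability, therefore the primary population for analysis is the safety population". The endpoints in section 3.1.1 begin with "Treatment Emergent Adverse Events (TEAEs), including information on seriousness, intensity, drug relationship and DLTs" and list no MTCA, MTSA or MACA. Under section 3.2.1.1, DLTs "will be summarised by treatment group and overall with the number and percentage of subjects with DLTs". Section 3.2.1 adds: "All safety data will be included in the data listings and summary tables will be based on the safety population". Section 3.2.22 sets the denominator: "Percentages will be calculated using a denominator of all subjects in a specified population and by treatment group". Section 3.2.25 mentions a Bayesian model only as an option at Safety Review Committee (SRC) meetings. Section 5 records no changes from protocol.

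**The concern.** The SAP is where the primary-endpoint analysis should be fixed in advance. Its readable text repeats that the aim is to find the MTCA, but then plans neither the set on which the protocol judges it nor the analysis that would report it. Whoever programs the outputs from this SAP would produce DLT tables on the safety population and stop there.

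The MTCA is defined by a 33% limit on subjects with a DLT, so the denominator matters. The protocol also expects some treated subjects to be non-evaluable: cohorts take three to five treated subjects to secure three who are evaluable (section 4.2.1.2), and those who leave early for reasons other than a DLT may be replaced (section 4.7.1.3). At stake is the final reporting of the primary endpoint, and the record of whether the departure was intended.

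**Working it through.** No stated sample size, power or error rate is in dispute, so there is no such figure to reproduce. The check compares the two texts and then works out what the choice of denominator does.

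**1. Protocol against visible SAP**

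| Protocol item | Visible SAP |
|---|---|
| MTCA/MTSA evaluation set (12.1) | Not in section 2; safety population named as primary (2.7) |
| DLT listings and incidence; table of DLT or grade 2 and above (12.2.4) | Carried over (3.2.1.1) |
| Exact 95% CI for categorical data (12.2.2) | None stated for DLTs |
| Final Bayesian model, two sets of priors, 90% credibility sets (12.2.4) | Absent; optional model at SRC meetings only (3.2.25) |
| Posterior summaries of MTCA and MTSA (12.2.4) | Absent |
| MTCA or MACA as primary endpoint (4.4.1.1) | Not among the endpoints (3.1.1); no reporting planned |
| Departure recorded | Section 5 records none |

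The SAP sends exploratory analyses to a dedicated SAP (3.1.4, 3.2.20) and dosimetry calculations to a Dosimetry Analysis Plan (3.1.3.3). It sends the MTCA analysis nowhere, and its table of contents shows no such section.

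**2. Which set the DLT percentages use**

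The DLT paragraph in section 3.2.1.1 names no population. Sections 3.2.1 and 3.2.22 together make it the safety population. The companion table of DLT or grade 2 and above is specified as numbers of subjects, without percentages.

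**3. Effect of the denominator (all counts assumed)**

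Let T be the number treated at a level, E the number in the 12.1 set and D the number with a DLT. If every DLT is in an evaluable subject:

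safety-population rate = D/T = (D/E) × (E/T).

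Exact 95% limits for x out of n are the 2.5% quantile of Beta(x, n−x+1) and the 97.5% quantile of Beta(x+1, n−x).

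- One cohort, T = 5, E = 3, D = 1. Safety population: 1/5 = 20.0% (0.5–71.6). 12.1 set: 1/3 = 33.3% (0.8–90.6). Check: 33.3% × 3/5 = 20.0%.
- Level repeated in a further cohort (optional under protocol 4.2.1.3), T = 10, E = 8, D = 3. Safety population: 3/10 = 30.0% (6.7–65.2). 12.1 set: 3/8 = 37.5% (8.5–75.5). Check: 37.5% × 8/10 = 30.0%.
- Reversal. T = 5, E = 3, one DLT in an evaluable subject, and another found at the early discontinuation visit of a subject who left for progression. The SAP counts DLTs up to that visit; 12.1 read literally leaves the second subject out. Safety population: 2/5 = 40.0%. 12.1 set: 1/3 = 33.3%.
- T = E: the two rates are identical.

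**4. Sensitivity of the model to the same choice**

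Attachment 5 gives logit p = logit p0 + [(logit 0.33 − logit p0)/MTSA]·d1 + β·d2, with p0 ~ Beta(1, 9), MTSA ~ Gamma(4, rate 0.5) and β ~ N(0, SD 0.25). Prior draws give MTCA probabilities of 31.6, 25.8, 15.7 and 27.0% in the four bands of Table 11, which states 32.5, 24.6, 15.7 and 27.2%. With assumed data of 0/3 at each of the four lower levels and 3 DLTs at 2×7.5 GBq:

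| Data at 2×7.5 GBq | Posterior mean DLT rate (90% set) | P(rate ≤ 33%) |
|---|---|---|
| 8 evaluable | 25.0% (8.3–46.8) | 76.2% |
| plus 2 dropouts, first dose only (d2 = 0) | 24.2% (8.0–45.5) | 78.5% |
| plus 2 dropouts, both doses | 21.6% (7.1–40.8) | 85.7% |

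**The case against.** The SAP does not ignore protocol 12.2.4: its descriptive DLT outputs are there. A safety-population DLT table is legitimate as a safety table and agrees with the safety set in protocol 12.1. The modelling is planned only where feasible, and during escalation it is triggered by reported DLTs (protocol 4.2.1.3). The MTCA is confirmed jointly by the SRC and the sponsor on all available data, not read off these tables. DLT n/N on the 12.1 set could be rebuilt from the DLT listings, withdrawal reasons and administration listings. The SAP appendices after Appendix 1 are blacked out and might hold an output shell.

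Much of this stands and limits the point. It does not remove it. Lack of feasibility may excuse an unfitted model, but not a missing set, an unreported MACA or a departure left undeclared. Protocol 12.2.4 plans an end-of-study analysis in addition to what is done at SRC meetings. A primary endpoint should not depend on unplanned reconstruction.

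Three stronger readings are tempting and are not supported:

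- A reader might infer that the safety-population rate is always too low. The reversal example shows otherwise.
- A reader might infer that the model-based MTCA would be biased in the same way. Neither document plans to fit the model on the safety population, and most of the contrast in step 4 appears only if both dropouts are assumed to have had the full second dose.
- A reader might infer that subjects given only the screening administration will dilute the DLT percentages. Section 2.3 says: "The safety population is all subjects who received at least one dose of study medication (including screening administration"). However, DLTs belong to the treatment period, post-screening adverse events are tabulated separately, and section 3.2.22 allows a denominator footnote. This needs a clarification only.

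**Conclusion.** The point holds for the visible text. The protocol's MTCA/MTSA set, final model, prior sensitivity analysis, posterior summaries and reporting of MTCA or MACA are all missing from the SAP, without referral elsewhere and without a declared change. That conclusion rests on the two texts, not on the size of any numerical shift.

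The numerical effect depends on counts the documents do not give. In the illustrations with no DLT among excluded subjects, the observed rate falls by 13.3 percentage points (33.3% to 20.0%) or 7.5 points (37.5% to 30.0%), with intervals so wide that neither rate is informative by itself. The effect is zero if all treated subjects are evaluable. The consequence is for final reporting of the primary endpoint. The documents do not support a claim that SRC escalation decisions would be wrong, or any estimate of how often the 33% limit would be crossed.

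**What to change.** 1. Add the protocol 12.1 set to SAP section 2 and assign the MTCA/MTSA evaluation to it in section 2.7.
2. Report DLT n/N by activity level on that set with exact 95% confidence intervals. Keep the safety-population DLT tables as supportive, with a footnote saying whether subjects given only the screening administration are in the overall denominator.
3. Add the section 12.2.4 analysis on the same set, if estimable, with both sets of priors and 90% credibility sets, and a statement of MTCA, or of MACA if MTCA is not identified.
4. If any of this is deliberately dropped, say so and justify it in SAP section 5.

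The cost is one population definition, one table, one model section (the model and the informative priors are already in Attachment 5; the noninformative priors need specifying) and one reported line. No extra patients, visits or procedures are needed.

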#### **3.2.1.1 Adverse events**

AEs will be coded using the Medical Dictionary for Regulatory Activities (MedDRA) latest version at Ipsen coding department at the time of corresponding database lock and NCI-CTCAE version 5.0 will be used for the grade's classification.

Listings will be presented by treatment group, subject, start date-time, primary system organ class, preferred term and reported term for all AEs recorded during the study, after IMP screening administration, for core trial, additional cycles and follow-up long term separately.

Listings of all AEs, serious adverse events (SAE), AEs leading to withdrawal and listing of deaths will also be presented.

TEAEs will be flagged (\*) in the listing of AEs and will be summarised.

A TEAE for the IMP screening administration is defined as any AE that occurs after the IMP screening administration if:

- It was not present prior to IMP screening administration and it had onset before the first dose of IMP during core trial, or
- It was present prior to receiving the IMP screening administration but the grade increased between IMP screening administration and the first dose of IMP during core trial,
- It was present prior to receiving the IMP screening administration, the grade is the same but the causality changed to "related" between IMP screening administration and the first dose of IMP during core trial.

A TEAE for the core trial period is defined as any AE that occurs during the core trial period of the study if:

- It was not present prior to first dose of IMP during core trial period and it had onset before the EOCT/ED visit, or
- It was present prior to receiving the first dose of IMP during core trial period but the grade increased between first dose of IMP during core trial period and EOCT/ED visit,
- It was present prior to receiving the first dose of IMP during core trial period, the grade is the same but the causality changed to “related” between first dose of IMP during core trial period and EOCT/ED visit.

A TEAE for the additional cycles period is defined as any AE that occurs during the additional cycles period of the study if:

- It was not present prior to EOCT visit and it had onset before the EOAC/ED visit, or
- It was present prior to EOCT visit but the grade increased between EOCT visit and EOAC/ED visit,
- It was present prior to EOCT visit, the grade is the same but the causality changed to “related” between EOCT visit and EOAC/ED visit.

A TEAE for the long-term follow-up period is defined as any AE that occurs during the long-term follow-up period of the study if:

- It was not present prior to EOCT/ED visit or EOAC/ED visit, or
- It was present prior to EOCT/ED visit or EOAC/ED visit but the grade increased between EOCT/ED visit or EOAC/ED visit and end of study,
- It was present prior to EOCT/ED visit or EOAC/ED visit, the grade is the same but the causality changed to “related” between EOCT/ED visit or EOAC/ED visit and end of study.

In addition, adverse events will be assigned to a specific cycle of treatment for core trial and additional cycles. This assignment will be based on the start date of the adverse event: if the AE start date is on or after the date of treatment X and before the date of treatment X+1 (or if the subject does not receive a treatment X+1 or the treatment X+1 date is missing), then the TEAE will be assigned to Treatment Cycle X.

An overall summary table of all AEs will be presented by treatment group and overall, by cycle (if applicable) and overall, after IMP screening administration, for core trial, additional cycles and follow-up long term separately. In addition, an overall summary table will be presented by pooling cycles from core trial and additional cycles.

TEAEs will be summarised by treatment group and overall with the number and percentage of subjects with AEs classified by primary system organ class and preferred term, by cycle (if applicable) and overall, after IMP screening administration, for core trial, additional cycles and follow-up long term separately. The number of occurrences of a TEAE will also be presented.

In addition, summary tables will also be presented for related TEAEs, SAEs, related SAEs, non-serious TEAEs, TEAEs by decreasing frequency, TEAEs by NCI-CTCAE worst grade (for NCI-CTCAE worst grade  $\geq 3$ ) and TEAEs by most serious causality (category related only).

Summary of TEAEs and related TEAEs will be also summarised by pooling cycles from core trial and additional cycles.

DLTs during cycle 1 or 2 (i.e. occurring between the first administration of Lu-3BP-227 and EOCT/ED) will be summarised by treatment group and overall with the number and percentage of subjects with DLTs classified by primary system organ class and preferred term. The number of occurrences of a DLT will also be presented.

The number of subjects with at least one DLT or NCI-CTCAE grade  $\geq 2$  (excluding hair loss) will be tabulated by treatment group and overall, by cycle and overall.

Listings of all DLTs will also be presented.

Depending on the number of cases, for all SAEs linked to COVID-19, a summary table will also be provided by treatment group and overall, presenting the number of patients by SOC and PT, by pooling core trial, additional cycles and follow-up long term. Listings of all SAEs linked to COVID-19 will also be presented.

In the event of multiple reports of the same preferred term being reported by the same subject, the NCI-CTCAE worst grade (grade 5 > grade 4 > grade 3 > grade 2 > grade 1) and the most serious causality (related > not related) will be chosen.

